This is a cohort study with a cross-sectional component for the primary aim executed independently at UAMS and Stanford University. The Liver Transplant Program at

Study Title: Usefulness of Controlled Attenuation Parameter (CAP) for the assessment of liver steatosis in liver donors
PI: [name], MSc, DSc
Institution: University of Arkansas for Medical Sciences

each participating center will identify study subjects during the process of liver allocation to their listed recipients. Criteria for recruitment are as follows:

Inclusion criteria – Liver Recipient

• Men and women, Age 18-years old to 80-years old inclusive

Inclusion criteria – Liver Donor

- Valid TE with Fibroscan 530, defined as:
 - At least 10 valid measurements
 - IQR/Median stiffness value <30% (only in cases with >7.1 kPa)

Exclusion criteria – Liver Recipient

• Patient did not undergo liver transplantation

Exclusion criteria – Liver Donor

- Donation after circulatory death (DCD)
- No liver biopsy obtained during organ procurement process

Investigational Approach

The chronological process of organ procurement and study is explained in Table below:

Clinical or Research Event	Standard of Care	Research Only
1. When a liver donor becomes available, and only after brain death is confirmed, the Arkansas Regional Organ Recovery Agency (ARORA) contacts the UAMS Transplant coordinator and notifies the transplant surgeon.	~	
2. The recipient next in the liver transplant waitlist is notified and is admitted to UAMS.	~	
3. A liver biopsy (snap frozen) is performed by the Organ Recovery Agency (when applicable) before procurement.	~	
4. The surgeon travels to perform the liver procurement.	~	

Study Title:	Usefulness of Controlled Attenuation Parameter (CAP) for the assessment of liver steatosis
	in liver donors
PI:	[name], MSc, DSc
Institution:	University of Arkansas for Medical Sciences

5. Fibroscan 530 is obtained before the procurement in the donor.		~
6. A second liver biopsy is obtained by the time of procurement (on formaldehyde). This is reviewed by UAMS pathologists.	~	
7. Transplantation occurs.	✓	
8. Patient is discharged from hospital and continues with outpatient visits (from biweekly to every three months as per UAMS' liver transplant guidelines).	•	
9. At one of the subjects' regularly scheduled follow-up appointments (3 to 6 months post-transplant), a second TE is performed, this time on the recipient (using either Fibroscan 502 or 530).		~

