10. Subject continues with per protocol follow up until retransplantation, death, or 5 years of follow-up.	~	

Before organ procurement, a Fibroscan-trained investigator will bring Fibroscan 530 to the bedside of donor. TE will be performed with either the M- or XL-probe depending on the skin to liver capsule distance (M-probe if <2.5 cm, and XL-probe when between 2.5 and 3.5 cm), as per manufacturer's recommendations (Echosens, Paris, France). In brief, after applying a water-based gel, the corresponding probe will be placed against the right hypochondrium at the level of the mid axillary line (exerting a slight pressure), and then 10 valid TE measurements will be obtained. The procedure should take no more than 5-7 minutes. Data from TE will be stored for future extraction of CAP. In order to assure an adequate fasting period before TE (\geq 3 hours) the surgeon leading organ procurement would request stopping of enteral nutrition after being initially contacted by the organ procurement organization (in the case of UAMS, the Arkansas Regional Organ Recover Agency [ARORA]), when applicable, and only after confirmation of brain death.

As part of the standard evaluation of the donor allograft a liver biopsy is obtained to address the degree of steatosis (one standard frozen core). Investigators will make sure this biopsy is performed by the time of TE. Only bedside biopsies on the mid-axillary line or biopsies from segments VI/VII after allograft procurement will be allowed. Although liver biopsies should ideally be performed immediately after

Study Title:	Usefulness of Controlled Attenuation Parameter (CAP) for the assessment of liver steatosis
	in liver donors
PI:	[name], MSc, DSc
Institution:	University of Arkansas for Medical Sciences

performing TE and before organ procurement, liver biopsies obtained from the time of donor identification and up until back table preparation (inclusive) will be acceptable. In all cases where the organ is allocated to a recipient, the transplant surgeon will be asked to grade the appearance of the liver before implantation.

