During liver transplant procedure and immediately after finalization of venous, arterial and biliary anastomoses, a second biopsy will be obtained (formaldehyde). This biopsy is taken routinely as part or the liver transplant protocol at UAMS to address quality of the implanted allograft including damage from reperfusion. The allograft site from which biopsy will be obtained will be left to the discretion of the transplant surgeon, although it should be documented in the operative note.

Before transplantation, the following data will be collected about the donor (data will be collected from the United Network for Organ Sharing [UNOS] portal, which compiles deidentified clinical data relevant to liver transplantation):

- height,
- weight,
- gender,
- age,
- ethnicity,
- cause of death,
- comorbidities,
- platelets,
- bilirubin,
- ALP,
- ALT and AST on the day of TE,
- peak ALT and AST,
- presence of any infectious disease
- degree of steatosis from snap frozen biopsy
- NPO status will be documented as well (in hours), from last oral intake or stopping of enteral nutrition to TE procedure,
- Cold and warm ischemia will be documented as part of the standard of care

On the day of transplantation, the following will be recorded from the transplant recipients:

• Routine labs on the day of transplantation (CBC, chemistry, liver panel, INR).

After transplantation, the following liver transplant outcomes will be prospectively documented:

• development of primary non-function (PNF),

Study Title: Usefulness of Controlled Attenuation Parameter (CAP) for the assessment of liver steatosis in liver donors

PI: [name], MSc, DSc

Institution: University of Arkansas for Medical Sciences

- early allograft dysfunction (EAD),
- peak ALT,
- ICU length of stay,
- retransplantation, and
- death.

PNF will be defined as AST>3000, plus INR ≥2.5 or arterial pH ≤7.30 within 7 days from implantation; whereas EAD as total bilirubin >10 mg/dL on day 7, INR ≥1.6 on day 7, and ALT or AST >2000 U/L during first week post-LT. Need for retransplantation or death at 3- to 6- months post-transplant (depending on follow up protocol at each participating center) will be recorded as well. Where available, a follow up TE with Fibroscan 502 or 530 will be performed at a standard-of-care follow outpatient visit at 3-6 months post-transplant. The patient will lie over his/her back and both the M and XL probes will be used following the same steps described above.

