All liver biopsies will be evaluated by two independent liver pathologists blinded to the results of CAP. In all cases, both the snap frozen and formaldehyde liver biopsy specimens will be reviewed and the degree of macrovesicular steatosis graded as per standard recommendations (<5, 5-33%, 34-66%, >66%). Liver pathologists will independently stage fibrosis of liver specimens using the Batts-Ludwig scoring system and the Brunt classification.

Data Analysis

The primary aim is to correlate the CAP results with the degree of hepatic steatosis on the liver biopsy fixed in formaldehyde. Spearman's rho will be used for this analysis. Parallel analyses will be performed with the snap frozen sample, and computerized histomorphometry to determine accuracy of CAP in different possible clinical scenarios. In order to assess whether a threshold value of CAP with a sufficiently high positive predictive value can be defined to obviate the need for a liver biopsy during organ procurement, Receiver Operating Characteristics (ROC) curves will be plotted, and areas under the curve (AUROC) reported as a measure of accuracy of CAP. For this analysis, the magnitude of steatosis in the formaldehyde samples will be dichotomized as \geq 34 or <34% in order to address steatosis as for EDC allografts. A sensitivity analysis using computed histomorphometry results and dichotomizing grading of steatosis as \geq 20 or <20% will be performed in case the prior analysis lacks power, as this degree of steatosis has been found to be associated with poor post-transplant outcomes as well.

Study Title:	Usefulness of Controlled Attenuation Parameter (CAP) for the assessment of liver steatosis
	in liver donors
PI:	[name], MSc, DSc
Institution:	University of Arkansas for Medical Sciences

CAP will be performed with either the M- or XL-probe depending on the skin to liver capsule distance (M-probe if <2.5 cm, and XL-probe when between 2.5 and 3.5 cm) as per manufacturer's recommendations (Echosens, Paris, France).

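### The biopsy used as the primary reference has no site rule, while the supporting frozen biopsy does, so the primary accuracy estimate may compare CAP with fat sampled elsewhere in the liver

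*Combined protocol and SAP*

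**What the plan says.** All references are to the combined protocol and SAP.

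- **Where CAP is read.** The Investigational Approach places the probe on the right hypochondrium at the mid-axillary line.
- **Frozen donor core.** The paragraph on the standard donor evaluation says "a liver biopsy is obtained to address the degree of steatosis (one standard frozen core"), and then sets a site rule: "Only bedside biopsies on the mid-axillary line or biopsies from segments VI/VII after allograft procurement will be allowed". It accepts biopsies taken up to and including back-table preparation.
- **Formaldehyde biopsy.** The next paragraph says that "immediately after finalization of venous, arterial and biliary anastomoses, a second biopsy will be obtained (formaldehyde"). On site it says: "The allograft site from which biopsy will be obtained will be left to the discretion of the transplant surgeon". The same sentence asks for the site to be recorded in the operative note.
- **Event table.** Step 6 of the table in the same section, listed before transplantation, says "A second liver biopsy is obtained by the time of procurement (on formaldehyde").
- **Role in the analysis.** The Data Analysis section states: "The primary aim is to correlate the CAP results with the degree of hepatic steatosis on the liver biopsy fixed in formaldehyde". The ROC analysis at 34% steatosis uses the formaldehyde samples too. The frozen sample serves parallel analyses only.
- **Use of site.** Biopsy site is not among the data items listed for donor or recipient, and no planned analysis uses it.

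**The concern.** The plan already treats sampling site as important enough to restrict, since it ties the donor core to the region that the probe interrogates. That restriction attaches to the supporting reference. The specimen that decides the primary result has none.

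If steatosis varies within a liver, a core taken away from the CAP window carries reference error unrelated to CAP. Such error lowers rho, AUROC and positive predictive value. The study asks whether CAP can stand in for a biopsy during procurement, so an understated accuracy bears directly on its main conclusion, and the planned analyses contain nothing that would reveal the cause.

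**Working it through.** **1. Which site rule covers which specimen**

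| | Frozen donor core | Formaldehyde biopsy |
|---|---|---|
| Site | Mid-axillary line, or segments VI/VII | Surgeon's choice, documented in the operative note |
| Timing, narrative | Donor identification to back-table preparation | After the anastomoses |
| Timing, event table | Before procurement (step 3) | By the time of procurement (step 6) |
| Role | Parallel analysis | Primary rho and the ROC at 34% |

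On the narrative timing, the formaldehyde biopsy falls after the last point accepted in the paragraph that holds the VI/VII rule, and it has its own sentence on site. On the event-table timing, it falls inside that window, and the general wording of the VI/VII rule could cover it. The specific sentence on the formaldehyde specimen makes the first reading the better one, but the text does not settle it.

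**2. Is there a planned figure to reproduce?**

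No stated number depends on biopsy site. The target of 100 transplanted livers comes without an expected rho or AUROC, alpha or power, so it cannot be used to judge how much attenuation the design can absorb.

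**3. Illustration of size**

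Assumptions, none of them from the documents:
- The site-matched rho is 0.60.
- The reliability R (squared correlation of off-site fat with fat in the CAP window) is 0.6 to 0.9.
- The added error is unrelated to CAP.

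Formula: observed rho = 0.60 × √R.

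- All specimens off-site, R = 0.9: 0.60 × 0.949 = 0.57, a loss of 5%.
- All specimens off-site, R = 0.6: 0.60 × 0.775 = 0.46, a loss of 23%.
- Uniform fat, R = 1: 0.60, no loss.

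If only a fraction f is off-site, and the choice of site is unrelated to fat content, observed rho is about 0.60 × [(1 − f) + f√R]. At f = 0.5 this gives 0.60 × (0.5 + 0.5 × 0.949) = 0.58 for R = 0.9, and 0.60 × (0.5 + 0.5 × 0.775) = 0.53 for R = 0.6.

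**4. Effect on AUROC**

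This was simulated with 1,000,000 bivariate-normal draws. Assumptions: 10% prevalence of steatosis of at least 34%, a CAP-to-window-fat correlation of 0.7, and a correlation k between the reference core and window fat (k = √R), applied to every liver.

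| k | Spearman's rho | AUROC |
|---|---|---|
| 1 | 0.68 | 0.87 |
| 0.95 | 0.65 | 0.86 |
| 0.9 | 0.61 | 0.84 |
| 0.8 | 0.54 | 0.80 |
| 0.7 | 0.47 | 0.77 |

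With a CAP-to-window-fat correlation of 0.5, rho falls from 0.48 to 0.34 and AUROC from 0.77 to 0.69 between k = 1 and k = 0.7. Across both settings, k from 0.95 to 0.7 costs about 5% to 30% of rho and about 0.01 to 0.11 of AUROC.

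**5. Cost of dropping off-site livers from the primary set**

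The Fisher-z standard error is 1/√(n − 3). If half of the 100 livers were off-site (assumed), the ratio is √(97/47) = 1.44, a 44% larger standard error. The plan also allows for a prevalence of high CAP as low as 5%, which is 100 × 0.05 = 5 livers before any are removed.

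**The case against.** The strongest reply has four parts.

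- **Discretion does not mean mismatch.** A reader might infer that the primary analysis does compare CAP with fat from another part of the liver. The documents do not support that. The surgeon may choose segments VI/VII, and nothing directs sampling elsewhere. Segments VI/VII are themselves only a regional match to the probe position. This stands, and the conclusion is limited to what may happen.
- **The site is not lost.** The sentence that grants discretion also asks for the site to be documented, so an analysis by site is possible. This stands, and it makes the remedy cheap. What is missing is a named data item and a planned analysis.
- **The site rule may already cover this specimen.** If the event-table timing is the intended one, the general VI/VII wording could apply and the asymmetry would shrink or vanish. This stands as a reason to reconcile the text. It does not dispose of the point, because the narrative says otherwise in terms specific to this biopsy.
- **The frozen-sample analysis is a check.** It is, in part. The plan runs it to examine CAP in different clinical scenarios, not to isolate a site effect. On the narrative timing, the two specimens can differ in site, fixation and timing together, so a gap between the two results could not be put down to site.

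**Conclusion.** The asymmetry is real and no planned analysis handles it: the plan controls site for the supporting reference but not clearly for the primary one. The primary rho and AUROC may therefore rest on fat sampled away from the CAP window. Where steatosis is uneven, the direction is towards understating accuracy.

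The size cannot be determined from the documents. A reader might take the 5% to 23% loss in rho as an estimate of this study's bias. It is not. It follows from an assumed rho of 0.60 and assumed reliabilities of 0.6 to 0.9, with every specimen off-site. It shrinks if only some are off-site and disappears if fat is uniform.

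A reader might also conclude that the primary analysis should be confined to VI/VII specimens. That does not follow either. It would discard livers from a sample of 100 with possibly very few positives, and it would select on a choice made by the surgeon. The point calls for clarification and a prespecified sensitivity analysis. It does not invalidate the primary aim.

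**What to change.** 1. Reconcile step 6 of the event table with the two narrative paragraphs on the timing and site of the formaldehyde biopsy. Either apply to the primary reference the site rule that the plan already uses for the donor core, or state why no rule is needed. Which site is clinically appropriate is for the investigators to decide. The narrative describes this biopsy as UAMS routine, so say whether the same holds at Stanford.
2. Add the biopsy segment, already due to be documented in the operative note, as a field in the study database.
3. Keep all livers in the primary analysis. Prespecify a sensitivity analysis of rho and AUROC restricted to formaldehyde specimens from segments VI/VII, and report the number of livers in it.

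The cost is a clarified paragraph, one data field and one further analysis. Intervals will be wider in the site-matched subset, by about 44% on the Fisher-z scale if half the livers qualify. No extra biopsy is needed.

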The first secondary aim is to examine correlation between TE results and fibrosis stage (Spearman's rho). In addition to correlating the TE results with fibrosis stage, we will explore whether the combination of CAP and TE results can define unacceptability and subsequently help in the decision to discard and organ. To achieve this goal a sensitivity analysis with various combinations of CAP and TE will be tested in logistic regression models, and then cut-off valued determined by constructing AUROC. Agreement between pathologist for both steatosis and fibrosis will be examined with the kappa statistic. A sensitivity analysis for donors on vasoactive amines or a peak ALT or AST >300 before procurement is planned to better determine accuracy of CAP/TE in liver donors.

The second secondary aim is to correlate CAP and TE results with various post-LT outcomes. Various (logistic, linear or proportional hazards) regression analyses will be used depending on the outcome variable of interest (PNF, EAD, retransplantation or death). Predictor variables will include CAP and TE as well as well-known donor and recipient predictors of LT outcomes (i.e. age, MELD, ICU-stay, etc).

The third secondary aim is to determine the change in CAP after LT. Baseline and follow up CAP determinations will be compared with paired t-test or Wilcoxon, depending on distribution of data. Normal distribution will be tested with Shapiro-Wilk. Categorical changes (i.e. \geq 34% to <34%) will be addressed with McNemar's test.

Accurate sample size determination is difficult in this pilot study because the test characteristics are not defined. We propose to examine as many donors as needed to achieve 100 transplanted liver allografts, which will allow detection of meaningful differences between livers with high versus low CAP values. If the prevalence of unacceptably high CAP value is as low as 5% of the livers, the sample size will permit detection of a threshold that has 80% positive predictive value or higher. Between the two participating institutions, it is expected to complete inclusion of 100 transplanted liver allografts in one year. It is expected to include no more than 60 patients at UAMS.

Data Collection and Handling

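### The time point for death and retransplantation can differ between the two centres, and the plan commits to no common horizon, model or centre adjustment that would allow for it

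*Combined protocol and SAP*

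**What the plan says.** - **Time of recording.** Investigational Approach first lists retransplantation and death, without a time limit, among outcomes to be documented prospectively. The outcome definitions then add: "Need for retransplantation or death at 3- to 6- months post-transplant (depending on follow up protocol at each participating center". Neither centre's own time point is given.
- **Longer follow-up.** Step 10 of the procedures table, marked standard of care, reads: "Subject continues with per protocol follow up until retransplantation, death, or 5 years of follow-up". The table is written around UAMS.
- **Model.** For the second secondary aim, Data Analysis states: "Various (logistic, linear or proportional hazards) regression analyses will be used depending on the outcome variable of interest (PNF, EAD, retransplantation or death". No model is assigned to any one outcome.
- **Predictors.** "Predictor variables will include CAP and TE as well as well-known donor and recipient predictors of LT outcomes". The examples given are age, MELD and ICU stay, followed by an open-ended etc. Centre and length of follow-up are not named.
- **Centres and size.** Study Design describes a study "executed independently at UAMS and Stanford University". Data Collection and Handling combines the two databases only after the study is completed. The target is 100 transplanted allografts, with no more than 60 patients expected at UAMS.

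**The concern.** A binary outcome means the same thing at two sites only if it is read over the same length of time. Here the reading time is tied to each centre's own follow-up protocol, anywhere from 3 to 6 months. A single status field per recipient, analysed by logistic regression, would fit the wording fully. A recipient who dies in month 5 would then count as an event at a 6-month centre and as a non-event at a 3-month centre.

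Two things are at stake, both for the aim of relating CAP and TE to outcomes after transplantation. First, the window can create a difference in risk between centres. If CAP also differs between centres, part of that difference can pass into the CAP coefficient. Second, events after the shorter window may be lost from an analysis that will have few events in any case. Because the databases are merged only at the end, a mismatch may not be noticed until it is hard to repair.

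**Working it through.** **The plan's own figure.** There is none to reproduce. The documents state no rate of death or retransplantation, no hazard shape and no centre-specific time. The sample-size statement concerns a CAP threshold and does not involve this window.

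**Inputs.** From the documents: two centres, 100 recipients, at most 60 at UAMS, hence 40 at the other centre if that limit is reached. Assumed: the extreme split (one centre at 3 months, the other at 6), a 3-month risk F3, and a Weibull shape k, where k = 1 is a constant hazard and k < 1 puts events early.

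**Step 1: risk ratio from the window alone.** F6 = 1 − (1 − F3)^(2^k). For F3 = 5% and k = 1, F6 = 1 − 0.95² = 9.75%, so F6/F3 = 1.95.

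| Shape k | F3 = 2% | F3 = 5% | F3 = 10% | F3 = 20% |
|---|---|---|---|---|
| 1.0 | 1.98 | 1.95 | 1.90 | 1.80 |
| 0.75 | 1.67 | 1.65 | 1.62 | 1.57 |
| 0.5 | 1.41 | 1.40 | 1.38 | 1.35 |
| 0.3 | 1.23 | 1.22 | 1.22 | 1.20 |

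Without any hazard model, the ratio is 1 divided by the share of 6-month events that fall by month 3. Shares of 70%, 80% and 90% give 1.43, 1.25 and 1.11. The hazard shape matters far more than the event rate. A common horizon, or censored time-to-event analysis, removes the window's contribution (ratio 1.0).

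**Step 2: what reaches the CAP estimate.** Suppose CAP has no true effect, its mean differs by 0.5 within-centre SD between centres, the split is 60/40, and centre is omitted. The slope of centre on CAP is 0.6 × 0.4 × 0.5 / (1 + 0.6 × 0.4 × 0.5²) = 0.12/1.06 = 0.113. The spurious CAP log odds ratio is approximately 0.113 times the centre log odds ratio.

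- k = 1, F3 = 5%: centre odds ratio (0.0975/0.9025)/(0.05/0.95) = 2.05. Spurious CAP odds ratio: exp(0.113 × ln 2.05) = 1.08.
- k = 1, F3 = 10%: centre odds ratio 2.11, spurious CAP odds ratio 1.09.
- k = 0.5, F3 = 5% or 10%: centre odds ratio 1.43 or 1.45, spurious CAP odds ratio 1.04.

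Large-sample simulation agrees: 1.08 and 1.09 at constant hazard, and 1.03 to 1.04 at k = 0.5. If the shorter-window centre has the higher CAP, the bias has the opposite sign. With centre in the logistic model, the CAP odds ratio returned to about 1 (0.99 at k = 1, F3 = 5%). Proportional hazards with censoring gave about 1.00 with no centre term.

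**Step 3: events left out.** Take F3 = 5%.

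- k = 1, 60 recipients at 3 months and 40 at 6: 60 × 0.05 + 40 × 0.0975 = 6.9 events, against 9.75 if all are read at 6 months (29% fewer).
- k = 1, split reversed: 40 × 0.05 + 60 × 0.0975 = 7.85 (19% fewer).
- k = 0.5 (F6 = 7.0%): 5.8 or 6.2 events against 7.0 (17% or 11% fewer).

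**The case against.** The strongest case against is that the plan already holds the remedy and that the harm is small.

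- **Proportional hazards is listed.** The choice of model depends on the outcome. PNF and EAD are first-week yes/no outcomes that suit logistic regression. Retransplantation and death are the natural candidates for proportional hazards, which deals with unequal follow-up by censoring. This stands as a likely intention, but the plan does not commit to it, gives no censoring rule, and does not say that dates of event and last contact are recorded.
- **The bias is minor.** With about 7 events among 100 recipients, the standard error of a log odds ratio per SD is roughly 1/√(6.9 × 0.931) = 0.39. The largest bias at F3 = 5%, ln 1.08 = 0.08, is about a fifth of that. This stands. The gain from the fix is a clearly defined endpoint and a fuller event count more than a large correction to CAP.
- **The list of predictors is open.** Centre could be added under the etc. That is true, but the plan does not say that it will be.

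Some stronger readings are tempting and are not supported. A reader might infer that one centre uses 3 months and the other 6; the text gives only a range. A reader might also infer that a centre effect in a logistic model is itself the harm. In fact, including centre protects the CAP estimate, and the risk lies in leaving it out. Nor do the documents show that later events are discarded: retransplantation and death are also listed as prospectively documented with no time limit, and step 10 continues follow-up to 5 years, at least as written for UAMS.

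**Conclusion.** The concern holds in a limited form. The rule makes the horizon for death and retransplantation depend on centre, and the permitted analysis need not allow for that, so following the plan can pool two different endpoints.

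The size is conditional. Under the extreme split, the window alone gives a risk ratio of about 1.1 to 2.0. A reader might take two-fold as the expected figure, but it is close to the upper limit unless the hazard rises over time, and it needs a constant hazard and low risk. Any less extreme split gives less.

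Nor do the documents support saying that the CAP association is confounded. They report no CAP difference between centres. It can be biased if there is such a difference and centre is omitted, by an odds ratio of about 1.03 to 1.09 under an assumed 0.5 SD difference. Between about 11% and 29% of 6-month events would go uncounted in the cases worked above, and fewer if events fall earlier still.

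This concerns one secondary aim of a study that calls itself a pilot. The primary comparison of CAP with histology is untouched. The change is still worth making, because it is cheap and removes the window problem whatever the true hazard shape.

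**What to change.** 1. In the outcome definitions under Investigational Approach, replace the centre-dependent 3- to 6-month reading with one 6-month horizon for death and retransplantation at both centres.
2. Record dates of transplantation, death, retransplantation and last contact for every recipient.
3. Under the second secondary aim in Data Analysis, state that these two outcomes are analysed by proportional hazards regression, censored at last contact or 6 months, whichever is earlier, and stratified by centre. Do not use logistic regression for them.
4. Reconcile the outcome definitions with step 10 of the procedures table ("until retransplantation, death, or 5 years of follow-up"), and say whether that step applies at both centres.

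The cost is a few sentences and a few date fields. Any centre now reading at 3 months would wait up to 3 more months for final data. Because the table is written around UAMS, the second centre must confirm that its routine follow-up reaches 6 months.
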